9.4.3 Serum immunoglobulin concentrations

Immunoglobulins (IgE, IgA and IgM) will be summarized by treatment group, RLZ total and visit for absolute values, change from Baseline, and percent change from Baseline.

Individual figures over time (absolute value) will be presented by study participant, with all variables overlaid on the same plot and separate plots each study participant.

Measurements BLQ will be imputed with half of the LLOQ for the purpose of calculating change from Baseline. Measurements ALQ, if applicable, will be imputed to the upper limit of quantification.

Immunoglobulins (IgE, IgA, and IgM) will be listed.

9.4.4 Anti-tetanus toxoid serum titers

Anti-tetanus toxoid serum titers will be summarized by treatment group, RLZ total and visit for both absolute values, change from Baseline, and percent change from Baseline.

The geometric mean change from Baseline with 95% CI in anti-tetanus toxoid serum titers versus time at each scheduled timepoint will be plotted by treatment group excluding all participants with undetectable Baseline titers. IgG values will be overlaid on the same plot.

Measurements BLQ will be imputed with half of the LLOQ for the purpose of calculating change from Baseline. Measurements, if applicable, will be imputed to the upper limit of quantification.

Anti-tetanus toxoid serum titers will be listed.

10 SAFETY ANALYSES

All safety analyses will be presented using the SS. Listings will be presented by treatment group and study participant; tabulations will be presented by treatment group and RLZ total.

Unless otherwise specified, safety analyses will be presented by treatment group as defined in [Section 3.6](#).

10.1 Extent of exposure

The number of weeks on IMP will be summarized by treatment group and RLZ total. The number of days on IMP will be calculated as follows:

$$\text{Number of weeks on IMP} = \frac{[(\text{Date of Last Dose Received}) - (\text{Date of First Dose Received}) + 1]}{7}$$

The total number of infusions will be summarized using descriptive statistics by treatment group and RLZ total. Categorical summaries of the number of infusions (1-6) will also be summarized.

The summaries above will be repeated excluding the mock infusions.

All drug administration details will be listed.

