Day (days) ^c	-28 to -1	1	3(±1)	8(±2)	15(±2)	22(±2)	24(±1)	29(±2)	36(±2)	43(±2)	57(±3)	71(±4)	85(±3)	99(±4)
Plasma complement levels (C3a and C5a) ⁿ		X							X					
MGFA classification	X	X								X				X
QMG scale	X	X		X	X	X		X	X	X		X		X
MG-C scale	X	X		X	X	X		X	X	X		X		X
MG-ADL	X	X		X	X	X		X	X	X	X	X	X	X
MG Symptoms PRO	X	X		X	X			X		X		X		X
PGI-S	X	X			X			X				X		X
PGI-C					X			X				X		X
EQ-5D-5L		X								X				
MGII ^o		X								X				
MG-QOL15r		X								X				
Study drug discontinuation criteria				X	X	X		X	X					
Study withdrawal criteria	X	X	X	X	X	X	X	X	X	X	X	X	X	X

AChR=acetylcholine receptor; ADA=anti-drug antibody; AE=adverse event; AESM=adverse events of special monitoring; BL=Baseline; C-SSRS=Columbia Suicide Severity Rating Scale; ECG=electrocardiogram; EQ-5D-5L=EuroQol-5D-5L; EOS=End of Study; EOT=End of Treatment; GI=gastrointestinal; HIV=human immunodeficiency virus; IgA=immunoglobulin A; IgE=immunoglobulin E; IgG=immunoglobulin G; IgM= immunoglobulin M; IGRA=interferon-gamma release assay; IMP=investigational medicinal product; INR=international normalized ratio; IRT=interactive response technology; MG=myasthenia gravis; MG-ADL=myasthenia gravis-Activities of Daily Living; MG-C=Myasthenia Gravis Composite; MGFA=Myasthenia Gravis Foundation of America; MGII=Myasthenia Gravis Impairment Index; MG-QOL15r=Myasthenia Gravis Quality of Life; MuSK=muscle-specific kinase; PEOT=premature end of treatment; PGI-C=Patient Global Impression of Change; PGI-S=Patient Global Impression of Severity; PK=pharmacokinetics; PTT=partial thromboplastin time; PRO=patient-reported outcome; QMG=Quantitative Myasthenia Gravis; TB=tuberculosis; V=Visit

^a This visit can be scheduled as a home visit, unless the study participant prefers to attend the site.

^b This visit will be a virtual visit, unless the study participant prefers to attend the site.

- ^c A visit window of ± 1 day is allowed for V3 and V7. A visit window of ± 2 day is allowed for all dosing visits. The visit window of ± 2 days is relative to the first dosing visit date. However, there should be a minimum interval of 5 days and maximum interval of 9 days as compared to the previous dose. A visit window of ± 3 days is allowed for V11 and V13. A visit window of ± 4 days is allowed for V12 and V14.
- ^d Refer to Section 1.4.
- ^e Only weight will be repeated at Baseline (V2).

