6 STUDY TREATMENTS

6.1 Treatments Administered

Study Treatment Name:	Rozanolixizumab (Treatment Arm 1)	Rozanolixizumab (Treatment Arm 2)	Placebo (Treatment Arm 3)
Dosage formulation:	Solution for infusion	Solution for infusion	Aqueous solution
Unit dose strength(s)/Dosage level(s):	[REDACTED]		0.9% sodium chloride aqueous solution (physiological saline, preservative free)
Route of Administration	Subcutaneous (sc)		
Dosing instructions:	
[REDACTED]
 
[REDACTED]
 
[REDACTED]
 
[REDACTED]
 
[REDACTED]
 
[REDACTED]
 
Bodyweight <50kg: dose to be administered [REDACTED]
 
Bodyweight ≥50kg and <70kg: dose to be administered [REDACTED]
 
Bodyweight ≥70kg and <100kg: dose to be administered [REDACTED]
 
[REDACTED]
 
Bodyweight ≥100kg: dose to be administered [REDACTED]
	
[REDACTED]
 
[REDACTED]
 
[REDACTED]
 
[REDACTED]
 
[REDACTED]
 
[REDACTED]
 
Bodyweight <50kg: dose to be administered [REDACTED]
 
Bodyweight ≥50kg and <70kg: dose to be administered [REDACTED]
 
Bodyweight ≥70kg and <100kg: dose to be administered [REDACTED]
 
[REDACTED]
 
Bodyweight ≥100kg: dose to be administered [REDACTED]
	6 sc doses of placebo at 1-week intervals
Packaging and Labeling	Rozanolixizumab and matching placebo are manufactured, packaged, and labeled according to Good Manufacturing Practice guidelines and applicable laws or regulations.		

Details on the preparation of study treatment for infusion, rate of infusion, administration, appropriate records handling, and blinded and unblinded site personnel roles are provided in the IMP Handling Manual. All site personnel delegated to handle study treatment storage, preparation and administration must be trained to IMP Handling Manual.

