Temporary treatment discontinuation due to low IgG levels may informally unblind the treatment assignment to the participant and site personnel. Therefore, infusions will be continued but given as mock infusions with only placebo irrespective of IMP designation. Allocation of mock kit numbers will be handled via the IRT. An unblinded Medical Monitor will inform the Investigator of the initiation of mock infusions and bring attention to any potential infection risk. The Medical Monitor will continue to review available safety information for these study participants (eg, AEs for infection and white cell count) while the IgG levels are at the protocol-defined low threshold values, and directly contact the Investigator should this review identify additional information that may be important in the care of the study participants. When the IgG levels have returned to the protocol-defined levels to re-initiate IMP (Section 7.1.4), the unblinded Medical Monitor will inform the Investigator of this decision. Based on the clinical situation, the Investigator has the option of holding the dose until deemed appropriate.

Further details are provided in the study manual and site blinding plan.

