10.2 Adverse events

10.2.1 Data considerations

Adverse events will be recorded from the time of informed consent until study completion. All AEs will be coded ([Section 3.8](#)).

In addition, AEs will be classified according to the Common Terminology Criteria for Adverse Events (CTCAE) Version 5 or later for severity. For any AEs where it is not possible to provide a CTCAE grading, the events will be assessed using a standard intensity classification (mild,

moderate and severe). For the purpose of the tabulations all CTCAE severity classifications will be mapped to a mild/moderate/severe grade as described below:

- Grade 1-- Mild
- Grade 2-- Moderate
- Grade 3, 4, 5-- Severe

These will be tabulated together with the AEs that were not classified according to CTCAE criteria i.e., all Grade 1 AEs as per CTCAE criteria will be included in the 'mild' category together with those AEs classified as mild as per the 'standard' intensity classification. In the case a mapped standard intensity classification per above rule is different from the standard intensity classification on CRF, the worst case will be used as the standard intensity classification (i.e. an AE with Grade 1 and moderate as intensity classification will be classified into moderate).

A TEAE is defined as an AE starting on or after the time of first administration of IMP up to and including 8 weeks (56 days) after the final dose. Adverse events starting before the date of the first administration of IMP or after 8 weeks following the final dose of IMP will not be considered TEAEs. Thus AEs before first dosing and AEs after 8 weeks following the final dose will be combined in one category. Such events will be listed only.

Where dates are missing or partially missing, AEs will be assumed to be treatment-emergent unless evidence exists that does not allow the AE to be treatment-emergent. Handling of missing dates for classification of AEs as TEAEs is described in [Section 4.2.2](#).

The following rules will be used to assign a TEAE to a study period:

- **Treatment Period:** a TEAE will be assigned to the Treatment Period for the tabulations if the start date of the event is on or after the date of the first administration of IMP on Day 1, up to 7 days following the final dose of IMP

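### SAP 10.1 credits the last weekly infusion with one day, so a full course reads 5.14 weeks; the mock-free duration also keeps mock weeks that are followed by active dosing

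*SAP*

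**What the plan says.** SAP 10.1 (Extent of exposure) states: "The number of weeks on IMP will be summarized by treatment group and RLZ total". The next sentence introduces the formula with "The number of days on IMP will be calculated as follows", but what follows is in weeks: last dose date minus first dose date, plus 1, divided by 7. The section also plans a summary of the total number of infusions, a categorical summary of 1 to 6 infusions, and a listing of all administrations. It then says: "The summaries above will be repeated excluding the mock infusions". It gives no separate definition of first or last dose for that repeat.

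The mock infusions come from Protocol 6.3.1.1. When IMP is held for low IgG, "infusions will be continued but given as mock infusions with only placebo irrespective of IMP designation". Protocol 7.1.4 allows IMP to resume once IgG has recovered, on the existing schedule and without make-up doses, so active infusions can follow mock ones.

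Elsewhere the SAP treats the week after an infusion as time on treatment. SAP 10.2.1 assigns TEAEs to the Treatment Period "up to 7 days following the final dose of IMP" and applies the same 168-hour rule to early withdrawals. SAP 6.4.2 assigns medications to the Treatment Period until the earlier of Day 43 and seven days after the last dose.

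**The concern.** Adding one day to the span between first and last dose suits a daily drug, where each dose covers one day. For a weekly infusion it leaves out six of the seven days that the SAP otherwise attributes to the last dose. The Treatment Period TEAE tables and the exposure table would then describe different lengths of time for the same participants, and nobody dosed on schedule could show six weeks of exposure in a six-week Treatment Period.

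The mock-free repeat raises a second problem. Its purpose is to show exposure to assigned treatment without the placebo infusions given during an IgG hold. A measure built only from a first and a last date cannot see a gap in the middle. Where active drug resumes after a hold, the duration would be presented as mock-free while still containing the mock weeks.

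**Working it through.** The plan states no expected exposure figure, so there is none to reproduce. The check applies the SAP 10.1 formula to the planned dosing days.

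**Inputs**
- Infusion days: Protocol 1.3 schedules study drug at Visits 2, 4, 5, 6, 8 and 9, nominal Days 1, 8, 15, 22, 29 and 36. Protocol 6.1 gives the spacing in the placebo column, "6 sc doses of placebo at 1-week intervals"; the corresponding active-arm text is blacked out.
- Window: "A visit window of ± 2 day is allowed for all dosing visits" (Protocol 1.3), so the sixth infusion falls on Days 34 to 38.
- Treatment Period: 6 weeks (SAP 3.2.2).
- On-treatment time after the last infusion: 7 days (SAP 10.2.1 and 6.4.2).

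**Step 1: full course.** (36 − 1 + 1)/7 = 36/7 = 5.14 weeks. With the window on the sixth infusion, the range is 34/7 = 4.86 to 38/7 = 5.43. Crediting seven days to the last infusion gives (36 − 1 + 7)/7 = 42/7 = 6.00 weeks.

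**Step 2: k weekly infusions without interruption.** The SAP formula gives (7(k − 1) + 1)/7 = k − 6/7 weeks. The seven-day version gives k weeks.

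| Infusions | SAP 10.1 (weeks) | With 7 days for last infusion | Shortfall |
|---|---|---|---|
| 1 | 0.14 | 1 | 86% |
| 2 | 1.14 | 2 | 43% |
| 3 | 2.14 | 3 | 29% |
| 4 | 3.14 | 4 | 21% |
| 5 | 4.14 | 5 | 17% |
| 6 | 5.14 | 6 | 14% |

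The absolute shortfall is 6 days in every row.

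**Step 3: mock-free repeat.** Drop the mock records and take first and last dose from what remains.
- Mock on Days 15 and 22, active on Days 1, 8, 29 and 36: (36 − 1 + 1)/7 = 5.14 weeks for four active infusions, the same as with no hold.
- Mock on Day 22 only: 5.14 weeks for five active infusions.
- Mock on Day 36: last active Day 29, 29/7 = 4.14 weeks for five active infusions.
- Mock on Days 29 and 36: last active Day 22, 22/7 = 3.14 weeks for four active infusions.

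**Step 4: how general this is.** Take the first infusion as active and let any of infusions 2 to 6 be mock. There are 2^5 − 1 = 31 patterns with at least one mock. If the sixth infusion is active, the duration is unchanged: 2^4 − 1 = 15 patterns. If the sixth is mock, it shortens: 2^4 = 16 patterns. Among the 15 patterns that form one unbroken mock run, 10 leave the duration unchanged and 5 shorten it. These are counts of possible patterns, not expected frequencies.

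If the last dose date is instead read as including mock infusions, the duration does not change in any pattern. SAP 10.1 does not settle which reading applies.

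**The case against.** The strongest reply is that first-to-last span plus one day is a consistent definition of dosing duration and contradicts no stated figure. The seven-day rule in SAP 10.2.1 assigns events to study periods and does not define exposure; the same section uses 56 days to decide whether an event is treatment-emergent. This is fair as far as it goes. The 56 days, however, include follow-up, whereas the seven-day rule marks the boundary of the Treatment Period itself, and SAP 6.4.2 draws the same boundary for medications.

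A reader might infer that the mock-free table merely repeats the ordinary one. The documents do not support that. The infusion counts are repeated without mocks and would correctly show four in the example above. The duration also falls when a mock run reaches the last infusion, provided last dose means last non-mock dose.

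A reader might also infer that safety comparisons are distorted, especially for early stoppers. That does not follow either. The shortfall is the same 6 days in every arm and is larger for early stoppers only as a percentage. Their infusion number is shown directly, and SAP 10.2 reports participants, percentages and event counts, with no exposure-adjusted rates.

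Finally, holds followed by active drug may be uncommon. Entry requires IgG above 5.5 g/L (Protocol 5.2) and a mandatory hold requires less than 1 g/L (Protocol 7.1.4), a fall of at least 1 − 1/5.5 = 82%. Protocol 4.2 describes slow recovery after single doses, with IgG back to Baseline by Day 57 on average, which points towards holds that run to the end of the course. The optional hold at 1 to below 2 g/L with infection needs a smaller fall, and the repeat-dose IgG reductions are blacked out. The frequency cannot be settled from the documents.

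**Conclusion.** The point holds as a minor correction to a descriptive safety table. At nominal dates, the SAP 10.1 formula reports 5.14 weeks for a full six-infusion course and 0.14 week for one infusion. Both are 6 days short of the time the SAP itself counts as on treatment, and the shortfall is equal in all arms. The mock-free duration fails to remove mock weeks that are followed by active dosing, and the first and last dose for that repeat are undefined.

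This rests on two assumptions: that exposure should match the SAP's seven-day Treatment Period rule, and that mock records are dropped before the dates are taken. No efficacy result, TEAE incidence or between-arm comparison changes. How many participants the mock issue touches is unknown.

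**What to change.** In SAP 10.1:
- Define weeks on IMP = (last infusion date − first infusion date + 7)/7. A full course then reads 6.00 weeks.
- For the mock-excluded duration, use the number of non-mock infusions × 1 week. This gives 4 weeks in the Days 15 and 22 example and 5 weeks for a single mock wherever it falls.
- Change days to weeks in the sentence that introduces the formula.

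Subtracting 7 days per mock infusion is not a safe alternative, because it double-counts once the last dose has moved to the last non-mock infusion. With mocks on Days 29 and 36, (22 − 1 + 7)/7 = 4 weeks, and subtracting 2 leaves 2 weeks for four active infusions.

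The revised main formula is still a span, so it includes any week in which a scheduled infusion was missed. The infusion counts already planned cover that. The cost is a few lines of SAP text and minor programming. No new data are needed, because all administration details are to be listed and mock kits are allocated through the IRT (Protocol 6.3.1.1).

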10.2 Adverse events

10.2.1 Data considerations

Adverse events will be recorded from the time of informed consent until study completion. All AEs will be coded ([Section 3.8](#)).

In addition, AEs will be classified according to the Common Terminology Criteria for Adverse Events (CTCAE) Version 5 or later for severity. For any AEs where it is not possible to provide a CTCAE grading, the events will be assessed using a standard intensity classification (mild,

moderate and severe). For the purpose of the tabulations all CTCAE severity classifications will be mapped to a mild/moderate/severe grade as described below:

- Grade 1-- Mild
- Grade 2-- Moderate
- Grade 3, 4, 5-- Severe

These will be tabulated together with the AEs that were not classified according to CTCAE criteria i.e., all Grade 1 AEs as per CTCAE criteria will be included in the 'mild' category together with those AEs classified as mild as per the 'standard' intensity classification. In the case a mapped standard intensity classification per above rule is different from the standard intensity classification on CRF, the worst case will be used as the standard intensity classification (i.e. an AE with Grade 1 and moderate as intensity classification will be classified into moderate).

A TEAE is defined as an AE starting on or after the time of first administration of IMP up to and including 8 weeks (56 days) after the final dose. Adverse events starting before the date of the first administration of IMP or after 8 weeks following the final dose of IMP will not be considered TEAEs. Thus AEs before first dosing and AEs after 8 weeks following the final dose will be combined in one category. Such events will be listed only.

Where dates are missing or partially missing, AEs will be assumed to be treatment-emergent unless evidence exists that does not allow the AE to be treatment-emergent. Handling of missing dates for classification of AEs as TEAEs is described in [Section 4.2.2](#).

The following rules will be used to assign a TEAE to a study period:

- **Treatment Period:** a TEAE will be assigned to the Treatment Period for the tabulations if the start date of the event is on or after the date of the first administration of IMP on Day 1, up to 7 days following the final dose of IMP
- **Observation Period:** a TEAE will be assigned to the Observation Period for the tabulations if the start date of the event is greater than 7 days after the date of the final dose of IMP until 8 weeks following the final dose; events starting later than 8 weeks following the final dose of IMP are not considered TEAEs

In the case of early withdrawal in the Treatment Period, a TEAE will be assigned to the Treatment Period based on the last received IMP plus 168 hours (7 days). Subsequent TEAEs (up to 8 weeks post-last dose) will be assigned to the Observation Period.

A TEAE will be counted as a TEAE related to IMP if the response to the question "Relationship to Study Medication" is "Related". Severe TEAEs are those with CTCAE Grade 3 or above, or those without a CTCAE grading classified as 'severe' by the Investigator.

Es will be presented as "number of study participants (percentage of study participants) [number of events]". In this style of output, "[number of events]" will include all cases of an AE including repeat occurrences in individual study participants, while "number of study participants" will count each study participant only once.

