8.3.1 Time period and frequency for collecting AE and SAE information

All SAEs will be collected from the signing of the ICF until the EOS visit at the time points specified in the Schedule of Activities (Section 1.3).

All AEs will be collected from the signing of the ICF until the EOS visit at the time points specified in the Schedule of Activities (Section 1.3).

All SAEs will be recorded and reported to the sponsor or designee within 24 hours, as indicated in Appendix 3 (Section 10.3). The Investigator will submit any updated SAE data to the sponsor within 24 hours of it being available.

The Investigator is specifically requested to collect and report to UCB (or its representative) any SAEs (even if the Investigator is certain that they are in no way associated with the study medication), up to 30 days from the end of the study for each participant, and to also inform study participants of the need to inform the Investigator of any SAE within this period. Serious AEs that the Investigator thinks may be associated with the study medication must be reported to UCB regardless of the time between the event and the end of the study.

The method of recording, evaluating, and assessing causality of AE and SAE and the procedures for completing and transmitting SAE reports are provided in Appendix 3 (Section 10.3).

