8.3.8 Treatment-emergent adverse events

Treatment-emergent AEs are defined as AEs starting after the time of first IMP administration up to and including 8 weeks after the final dose.

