9.5 Planned Safety and other Analyses

9.5.1 Safety analyses

The frequency and severity of all TEAEs will be presented for each treatment group separately by System Organ Class, high level term, and preferred term (Medical Dictionary for Regulatory Activities [MedDRA][®]). The data will be displayed as number of study participants experiencing the TEAE, percentage of study participants, and number of TEAEs. A TEAE is defined as any event that was not present prior to the first administration of IMP or any unresolved event already present before the first administration of IMP that worsens in intensity following exposure to treatment.

Laboratory evaluations and vital signs as well as ECG data will be analyzed over time. All safety analyses will be listed and summarized for the SS.

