- A "reasonable possibility" of a relationship conveys that there are facts, evidence, and/or arguments to suggest a causal relationship, rather than a relationship cannot be ruled out.
- The Investigator will use clinical judgment to determine the relationship.
- Alternative causes, such as underlying disease(s), concomitant therapy, and other risk factors, as well as the temporal relationship of the event to study medication administration will be considered and investigated.
- The Investigator will also consult the Investigator’s Brochure (IB) in his/her assessment.
- For each AE/SAE, the Investigator **must** document in the medical notes that he/she has reviewed the AE/SAE and has provided an assessment of causality.
- There may be situations in which an SAE has occurred and the Investigator has minimal information to include in the initial report to UCB. However, **it is very important that the Investigator always make an assessment of causality for every event before the initial transmission of the SAE data to UCB.**
- The Investigator may change his/her opinion of causality in light of follow-up information and send an SAE follow-up report with the updated causality assessment.
- The causality assessment is one of the criteria used when determining regulatory reporting requirements.

Follow-up of AEs and SAEs

- The Investigator is obligated to perform or arrange for the conduct of supplemental measurements and/or evaluations as medically indicated or as requested by UCB to elucidate the nature and/or causality of the AE or SAE as fully as possible. This may include additional laboratory tests or investigations, histopathological examinations, or consultation with other health care professionals.
- An AE should be followed until it has resolved, has a stable sequelae, the Investigator determines that it is no longer clinically significant, or the participant is lost to follow-up. This follow-up requirement applies to AEs, SAEs, and AEs of special interest.
- If a participant dies during participation in the study or during a recognized follow-up period, the Investigator will provide UCB with a copy of any post-mortem findings including histopathology.
- New or updated information will be recorded in the originally completed CRF.
- The Investigator will submit any updated SAE data to UCB within 24 hours of receipt of the information.

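### The plan holds conflicting TEAE definitions, and the SAP's start-date rule leaves screening-period events that worsen on treatment out of the TEAE tables unless the site opens a new record

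*SAP*

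**What the plan says.** Three places define a treatment-emergent adverse event.

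- **Protocol 9.5.1 (Safety analyses)** has two limbs: an event absent before first dose, and "any unresolved event already present before the first administration of IMP that worsens in intensity following exposure to treatment". It states no closing window.
- **Protocol 8.3.8 (Treatment-emergent adverse events)** has one: "Treatment-emergent AEs are defined as AEs starting after the time of first IMP administration up to and including 8 weeks after the final dose".
- **SAP 10.2.1 (Data considerations)** has one: "A TEAE is defined as an AE starting on or after the time of first administration of IMP up to and including 8 weeks", counted from the final dose. It then rules that "Adverse events starting before the date of the first administration of IMP or after 8 weeks following the final dose of IMP" do not count as TEAEs, and adds: "Such events will be listed only".

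Two further passages bear on how such events reach the database. Protocol 8.3.1 says "All AEs will be collected from the signing of the ICF until the EOS visit", so screening events are captured. Among the follow-up instructions in Protocol 10.3.3 is: "New or updated information will be recorded in the originally completed CRF".

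SAP 1 says that changes from the protocol's analyses are documented in SAP 3.9. That list runs from a week-to-day change in an interaction term to a revised Hy's Law definition. It has no entry on the TEAE definition.

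**The concern.** Occurrence of TEAEs and TEAEs leading to withdrawal of study drug are the two secondary safety endpoints (SAP 2.2.3.1). Both depend on the TEAE flag. So do the any, severe and related incidence tables, the treatment-emergent AESM and AESI tables (SAP 10.2.2) and the adverse-events-of-focus tables (SAP 10.2.3).

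The two rules classify the same participant differently. Take a mild headache that begins in screening, is still present at first dose, and becomes severe on treatment. Under Protocol 9.5.1 it is a TEAE. Under SAP 10.2.1, if the record keeps its screening start date, it is not a TEAE and appears only in a listing. Headache and gastrointestinal disturbance are the most common reactions named in Protocol 2.3, so this kind of event is where a difference could arise.

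**Working it through.** No figure in the plan needs reproducing. The check compares the texts, followed by an illustration of size.

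**Step 1: the definitions side by side.**

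| | Starts after first dose | Starts before, worsens after | Window |
|---|---|---|---|
| Protocol 9.5.1 | TEAE | TEAE | none stated |
| Protocol 8.3.8 | TEAE | not included | 8 weeks after final dose |
| SAP 10.2.1 | TEAE | excluded, listed only | 8 weeks after final dose |

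The SAP matches Protocol 8.3.8 in substance and departs from 9.5.1 in the middle column. Its exclusion is explicit. SAP 3.9 does not record the departure.

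**Step 2: can such events exist?** Yes. Events are collected from consent, and screening lasts up to 28 days.

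**Step 3: what start date would a worsened event carry?** The text points both ways.

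- Toward the original date: Protocol 10.3.3 sends updated information to the original form.
- Toward a new date: Protocol 10.3.1 makes exacerbation of a pre-existing condition an adverse event, and Protocol 8.2.1 has worsened examination findings recorded as adverse events.
- Nothing available says whether a rise in intensity opens a new record. Protocol 10.1.6.1 refers to eCRF Completion Guidelines, which are not among the documents.

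So a worsening updated in place is excluded, and one entered as a new event with a post-dose onset is counted.

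**Step 4: which outputs are affected?** The TEAE-based incidence tables, for records with a known pre-dose start. There are two exceptions. Missing or partial dates default to treatment-emergent (SAP 10.2.1), and the all-deaths row of the overview table is not restricted to TEAEs (SAP 10.2.2).

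**Step 5: direction.** Let *a* be the proportion of an arm with an event ongoing at first dose and updated in place. Let *w* be the proportion of those that worsen. The rule removes *a × w* from each arm. With equal *a* by randomization, the excess removed is *a × (w_drug − w_placebo)*. In expectation this is positive only if the drug aggravates existing events.

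**Step 6: size, under assumed rates.** The documents give neither *a* nor *w*. Assume *a* = 5–10% and *w* = 10–30%. SAP 2.4 gives 30 per arm in Stage 1 and 30–50 in Stage 2, so 60–80 for an arm that continues through both.

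- Low: 0.05 × 0.10 = 0.005; 0.005 × 60 = 0.3 participants.
- High: 0.10 × 0.30 = 0.03; 0.03 × 80 = 2.4 participants.

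That is about 0 to 2 per arm. For the any-TEAE row it is an upper figure under these rates, because a participant with another TEAE is still counted.

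**The case against.** The strongest reply is Protocol 8.3.8. It is the subsection dedicated to the definition, and the amendment history says Amendment 1 added it to make the definition clear. The SAP follows it closely, including the 8-week window that 9.5.1 lacks. A reader who sees only 9.5.1 and the SAP might infer that the SAP dropped the protocol's definition. The documents do not support that: the protocol has two definitions, and the SAP uses one of them. What remains is that the protocol's safety-analysis section says something else, and the choice is neither explained nor declared.

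The second reply is that sites may enter a worsening as a new event. A reader might infer that such events vanish from every TEAE table. That goes too far, because the follow-up line in Protocol 10.3.3 is general and does not address intensity or onset dating. The reply does not remove the point, though. It means that classification depends on site practice.

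Third, a reader might infer that the rule can only lower the rozanolixizumab count relative to placebo. It cannot be put that strongly: spontaneous worsening on placebo is removed too, and with counts this low the observed difference could move either way.

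Fourth, the events are not lost. They are listed, and the listings of AESMs, AESIs, deaths and withdrawals due to adverse events are not worded as TEAE-only. That is true, but listings do not feed the comparison by arm.

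**Conclusion.** The point holds as a conflict between definitions with a possible undercount. Protocol 9.5.1 counts pre-dose events that worsen after exposure; Protocol 8.3.8 and SAP 10.2.1 do not; SAP 3.9 is silent. A screening event updated in place to a higher intensity would be missing from the incidence tables behind both secondary safety endpoints.

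The consequence rests on two conditions that the documents leave open: that sites update the record rather than open a new one, and that some events ongoing at first dose do worsen. The direction, understating the excess over placebo, is an expectation that holds only if the drug aggravates existing events. The size cannot be derived from the documents. The range of about 0 to 2 participants per arm comes from assumed rates and is probably small for overall TEAE counts. It would matter most where counts are low, such as severe headache, but no count is available to show that it does.

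It is still worth correcting, because the same event can be classified in two ways in a secondary safety endpoint and the repair is cheap.

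**What to change.** 1. **SAP 10.2.1:** add that an adverse event ongoing at first dose whose intensity (CTCAE grade, or CRF intensity) increases after first dose and within the 8-week window is a TEAE, dated from the worsening. Use that date when assigning the event to the Treatment or Observation Period, since the present assignment uses the event's start date. Amend the listing-only sentence to match.
2. **Protocol 8.3.8 and 9.5.1:** reconcile them to one definition with one window. Changing the SAP alone would align it with 9.5.1 and leave it at odds with 8.3.8.
3. **SAP 3.9:** record the outcome. If the sponsor prefers the start-date rule, declare and justify it there as a departure from 9.5.1.
4. **eCRF completion guideline:** state that an increase in intensity after first dose either opens a new record or has its date recorded on the existing one. Without that date, item 1 cannot be programmed reliably.

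The cost is a few sentences, a CRF completion note and minor programming. TEAE counts may rise slightly in all arms.
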